6. Total number of subjects that failed screening (if not applicable, state N/A): 0

7. Total number of participants accrued since the beginning of the project: 26

8. For multi-center studies, number of subjects approved for accrual study-wide (SLU site plus all other sites):

9. For multi-center studies, number of subjects enrolled study-wide (SLU site plus other sites):

10. Number of withdrawals from the research and explanation/reasons for withdrawals.
N=9; Due to lack of patient returns at 4 months post repair for digital pictures to be obtained and for wound check

11. Description and number of:

Protocol Title: Conservative versus Suture Repair of Hand and Feet Lacerations in Children

a) Reportable Protocol Deviations/Violations since the last approval date:

none

b) Unanticipated Problems (UPs) since the last approval date:

none

c) Serious Adverse Events (SAEs) since the last approval date: Note: Information here should be consistent with the cumulative table, which should also be attached in section #16.

none

12. Have there been any complaints about the research during the last year?

N

If yes, please describe.

13. Briefly describe the progress of the study to date. Provide a status of participants in study, for example, where is the most recently accrued participant in terms of timeline in the study? If participants are in long-term follow-up, explain what this consists of in terms of data collection and/or intervention. Provide any new information in regard to risks. Summarize or attach publications or presentations.

Lack of patient follow up has hampered the progress of the study

14. Is there a Data Safety Monitoring (DSM) plan for this study?

Y No

Yes, a copy of the DSM report(s) for the last approval period is attached.

Yes, but a copy of the DSM reports(s) for the last approval period is not attached. Please explain below.

15. FDA Regulated Studies

Is this a Food and Drug Administration (FDA) Regulated Study, (i.e., involves drugs, N devices, biologics)? If yes, please answer the following questions:

a) Have there been any changes in the FDA status of any drug or device used in the study?

If yes, please explain:

b) Have any of the investigational drugs or devices used in this study received FDA approval?

If yes, please explain:

Protocol Title: Conservative versus Suture Repair of Hand and Feet Lacerations in Children

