
Please save frequently

b) Describe any animal experimentation and findings leading to the formulation of the study, if

Protocol Title: Conservative versus Suture Repair of Hand and Feet Lacerations in Children

there is no supporting human data.

n/a

2. Purpose of the study

a) Provide a brief lay summary of the project in <200 words. The lay summary should be readily understandable to the general public.

The purpose of this study is to compare outcomes of 2 repair methods in simple (<2cm) hand and feet lacerations in the pediatric population (2-17 yrs). Our hypothesis is that there is no statistical difference in cosmetic outcomes between suture repair and non-repair of these injuries. This study has been performed in the adult population, but has not yet been done in children. We would like to be the first to show that conservative repair can be done in our pediatric population. The suture group will have their injuries repaired with non-absorbable sutures (nylon) which remain the gold standard in cosmetic repair of hands and feet. The conservative group will have identical cleaning and preparation of the wound, but the laceration will be covered with antibiotic ointment and sterile gauze without repair. Secondary outcome measure include patient satisfaction, infection rates, pain during repair, time of initial ED visit stay, and cost of supplies used in repair. Our patients will return in 7-10 and 14 days and in 3 months for evaluation. Wounds and scars will be evaluated at both 7-10 and 14 days and 3-4 months by both the researchers and the parents or care givers. A satisfaction survey will be administered to the parent or guardian. At 3-4 months, digital photographs of the healing lacerations will be graded for appearance by clinicians blinded to the repair method. The initial visit will be billed to their insurance and the follow-up visits will be free (non-registered).

Page numbers from a sponsor's protocol/grant may be referenced in 2b and 2c.

b) List your research objectives (specific aims & hypotheses of the study).

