c) If the proposed study is a clinical trial where a drug, vaccine, device or other treatment is compared to a placebo group or comparison treatment group, what are the guidelines or endpoints by which early decisions regarding efficacy or lack of efficacy can be made? For example, it may be reasonable to stop enrollment on a study when efficacy has already been clearly demonstrated, to avoid unnecessary enrollments of additional subjects. Alternatively, it may be reasonable to stop enrollment when it is clear that efficacy will never be demonstrated, given the statistical power of the study as designed. Describe the guidelines that are in place to assist in making these determinations, if relevant to the proposed study.

On an ongoing basis, we will evaluate potential complications and if we identify serious complications related to the study group, we will consider study termination.

d) Describe how data analysis will be performed (statistical tests, methods of evaluating data) and indicate the smallest group/unit for which separate reporting will occur. For studies involving a questionnaire, if data and reliability information are available, please describe or provide references. For full board, unfunded studies describe sample size determination and power analysis. If none, please justify.

Differences between groups will be analyzed using the Student's t-test for independent samples. Proportions will be compared using chi-square and the z-test for independent proportions. A significance level of 0.05 will be used in all analysis. Since this is an equivalence trial, a non-inferiority average difference of 15mm with the cosmesis VAS scale will be considered clinically equivalent. Previous studies have determined that the minimal clinically important differences between two groups ranged from 10 to 15mm (4,15,16).

A sample size of 18 patients per group will be needed to provide a power of 90% with 0.05 alpha error to detect a 15mm difference in the VAS. A patient attrition rate of 40% is expected and with this considered, a total of 50 patients will be enrolled in order to power the study this will include the 20 patients already enrolled in the previous study (#23300).

Protocol Title: Conservative versus Suture Repair of Hand and Feet Lacerations in Children

Please save frequently

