4	Continuing Review	
Question 17 of the Continuing Review Form describes an amendment to the protocol that has not yet been submitted for review/approval. Please remove this information from Question 17 of the Continuing Review Form, and describe these requested change in questions 19-24 of the Continuing Review Form. In addition, please be sure to incorporate the changes throughout the protocol and consent documents, as applicable.
 
There is very limited information in question 17 regarding the proposed changes. Please be sure to describe the crowd-sourcing data considerations as it pertains to outcomes, consent changes, validity related to this type of wound repair. Please also describe how experimental design and primary/secondary outcomes for this study can incorporate the Amazon Mechanical Turk.
 
In addition, question 17 states the incorporation of mTurk is necessary in order to salvage this study. If these changes are not made, please describe how the study plans to accrue more subjects and obtain adequate follow-up data.
 
Done
	Y
5	Continuing Review	
Please provide an explanation as they why follow-up data was able to obtained for the first 18 subjects, but not for the last 9 subjects.
 
Uncertain as to why we could not get patients to return for a follow up 4 month visit, gift cards were still valid. It is this reason that we are changing the data analysis
	Y
3	Continuing Review	
Question 14 of the Continuing Review Form states there is no Data Safety Monitoring Plan for this study. However, section 9-11b of the protocol includes a plan for Data Safety Monitoring. Please revise the response to this question.
 
Since no further patient enrollment will take place and only the method of data analysis will change there is no further reason to have a DSM plan going forward
	Y
Additional Response by

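### Section 3d sets a 15 mm equivalence margin but names only a t-test of difference, and its own enrolment and attrition figures do not deliver the stated 90% power

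*Combined protocol and SAP*

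**What the plan says.** Section 3d gives the test, the margin and the sample size.

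- Test: "Differences between groups will be analyzed using the Student's t-test for independent samples", at a significance level of 0.05 with sidedness not stated.
- Margin: "Since this is an equivalence trial, a non-inferiority average difference of 15mm with the cosmesis VAS scale will be considered clinically equivalent".
- Sample size: "A sample size of 18 patients per group will be needed to provide a power of 90% with 0.05 alpha error", the target being detection of a 15 mm VAS difference. No SD is given. Attrition of 40% is expected and 50 children are to be enrolled; "this will include the 20 patients already enrolled in the previous study (#23300").

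The lay summary (section 2a) puts the hypothesis this way: "Our hypothesis is that there is no statistical difference in cosmetic outcomes between suture repair and non-repair of these injuries".

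The 2019 Continuing Review form adds the accrual position. Question 7: "Total number of participants accrued since the beginning of the project: 26". Question 10, on withdrawals: "N=9; Due to lack of patient returns at 4 months post repair for digital pictures to be obtained". In the Comments section, item 5, the Board counts 18 children followed and 9 not. The reply to item 3, on the data safety monitoring plan, says "Since no further patient enrollment will take place and only the method of data analysis will change". The Event History shows that form withdrawn on 09/30/2019.

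**The concern.** Three framings sit together in 3d: equivalence, non-inferiority, and detecting a difference. None is tied to a decision rule. The text does not say that a confidence interval will be compared with 15 mm, and the hypothesis in 2a is one that a non-significant t-test would appear to confirm. Failing to find a difference is not evidence that the difference is small, and it becomes easier as the trial shrinks. At stake is an inconclusive trial being reported as showing that unsutured wounds in children heal with an equivalent scar.

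The power statement has a separate fault that can be seen in 3d alone: the planned enrolment and the planned attrition do not produce the number of evaluable children on which the 90% rests.

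**Working it through.** **Inputs.** From 3d: 18 per group, power 90%, alpha 0.05, difference and margin 15 mm, 50 enrolled, 40% attrition. From the Continuing Review form: 26 accrued, 9 without the 4-month photograph. From Comments item 5: 18 followed, 9 not. Assumed: near-equal arms and a common SD.

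**Step 1: the plan's own figure.** Without an SD the 18 per group can be neither confirmed nor refuted, so the SD was solved from it. With df = n1 + n2 − 2 and λ = 15 / (SD × √(1/n1 + 1/n2)), two-sided power is P(|T| > t(0.975, df)), where T is noncentral t with noncentrality λ. Power 0.90 at 18 v 18 gives SD 13.5 mm. A one-sided 5% test gives 15.1 mm.

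**Step 2: evaluable children.**
- Needed: 2 × 18 = 36.
- From 3d's enrolment and attrition: 50 × 0.60 = 30. Reaching 36 would take 36 / 0.60 = 60.
- From the Continuing Review form: 26 − 9 = 17. The Board's count is 18, but 18 + 9 = 27, not 26.

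**Step 3: results at SD 13.5 mm.** SE = 13.5 × √(1/n1 + 1/n2). The false-equivalence columns take a true difference of 15 mm. The equivalence rule is two one-sided 5% tests, which is the same as the 90% CI lying inside ±15 mm.

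| Arms | SE (mm) | λ | t(0.975) | Two-sided power | Non-significant t-test, true 15 mm | 90% CI inside ±15 mm, true 15 mm | Equivalence power, true 0 |
|---|---|---|---|---|---|---|---|
| 18 v 18 | 4.50 | 3.33 | 2.032 | 90% | 10% | 5.0% | 90% |
| 15 v 15 | 4.93 | 3.04 | 2.048 | 84% | 16% | 5.0% | 81% |
| 9 v 9 | 6.36 | 2.36 | 2.120 | 60% | 40% | 4.8% | 46% |
| 9 v 8 | 6.56 | 2.29 | 2.131 | 57% | 43% | 4.7% | 41% |

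**Step 4: sensitivity.**
- One-sided 5% test, SD 15.1 mm: 84% at 15 v 15, and 62-65% at 17-18 children.
- 9 v 8 at SD 10 mm: two-sided power 82%, equivalence 81%, non-significant at a true 15 mm 18%. At SD 20 mm: 30%, 4% and 70%.
- If the 20 children from the previous study are additional to the 26, with 20 × 0.60 = 12 to 20 of them evaluable (assumed), totals are 17 + 12 = 29 to 17 + 20 = 37 and two-sided power is 82-91%.

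**The case against.** The 90% is a prospective design figure for 36 children, and under-accrual does not make a design figure wrong. That is right. The complaint about the 90% therefore rests on 3d's own attrition arithmetic and not on the 2019 accrual.

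It can also be said that the margin sentence already supplies the rule. It gives a number, but not what is compared with it. If it were the observed mean difference, a true difference of 15 mm would fall under the margin about half the time by symmetry, which is no protection.

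A reader might infer that the trial has ended with 17-18 evaluable children and cannot show equivalence. The documents do not establish this. Closure is stated in a reply about safety monitoring, on a form later withdrawn. Question 1b of that form appears with both the open-to-accrual and the on-hold boxes marked, possibly through text extraction. It is not stated whether the children from the previous study are within the 26. Counting them inside is the natural reading, because the form sets 26 against an approved 50 that includes them, but across both readings power runs from 57% to 91%. Even at 9 v 8, equivalence power is 81% if the SD is 10 mm.

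A reader might also infer that the proposed crowd rating on a Likert scale has left the 15 mm margin with nothing to apply to. Questions 20 and 21 put it tentatively and do not say that the physicians' VAS is dropped. The Board had already asked, in Comments item 4, how the outcomes would incorporate it. The reply says only that this was done, and question 23 still answers that the protocol needs no modification. The gap is real only if that rating becomes the primary outcome.

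**Conclusion.** Two points stand on the current text of 3d, whatever happened to enrolment. First, the equivalence claim has no decision rule, and the named test permits a non-significant result to be read as equivalence. At the implied SD that error is 10% at the intended 36 children and 16% at the 30 that 3d's figures yield, against 5% or less when the CI is judged against the margin. Second, 30 evaluable children give about 84% power, not 90%.

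The much larger error of 40-43%, and the fall in power to 57-60% (41-46% for two-sided equivalence), are conditional on closed enrolment, on the 26 including any children from the previous study, and on the back-solved SD of 13.5 mm. They are a reason to settle the count and should not be stated as the trial's outcome.

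**What to change.** In section 3d:

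1. State whether the aim is equivalence or non-inferiority. Base the conclusion on the CI for the difference between arms, at a stated level, against the 15 mm margin: both limits for equivalence, one for non-inferiority. Say that a non-significant t-test will not be read as equivalence, and bring the hypothesis in 2a into line.
2. State the assumed SD and restate the power for 30 evaluable children. If enrolment is closed, reconcile 17 with 18, say whether the children from the previous study are within the 26, and report the CI width for the children actually evaluable.

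Only if crowd rating is pursued as the primary outcome: keep the 100 mm VAS, or set a Likert margin before any rating, and amend the protocol as the Board asked in Comments item 4.

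Items 1 and 2 cost wording and a less favourable stated power, with no new patients, visits or procedures. The conditional item would need a protocol amendment and IRB approval.

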*** Continuing Review ***

Continuing Review Request

WHAT TO UPLOAD WITH YOUR CONTINUING REVIEW APPLICATION

For studies where research activities are limited to data analysis, upload subject safety information and publications (e.g., manuscripts, abstracts) since the last IRB approval, if applicable.

NOTE: if activities are limited to data analysis of de-identified/anonymous data (data that can no longer be linked to subject identifiers directly or through use of a code with master list kept), the study can likely be closed via the Final Report Form. See the SLU IRB Guidance for Closure of Human Subjects Research Studies.

For all other studies, upload:

- Subject safety information including the most current Serious Adverse Event (SAE) cumulative table and data safety monitoring reports since the last IRB approval, if applicable.
- Any publications (e.g., manuscripts, abstracts) since the last IRB approval.

Any changes, updated and/or new study materials should be uploaded and questions 19 - 24 of this form should be completed.

1. Please indicate the status of the study:

a) The study has not started but will become active.
Please explain why the study has not started.

b) X The study is ACTIVE (please check the appropriate box below):
 X Study is open to accrual.
 X Study is on hold or halted.
Please explain what needs to occur before accrual can resume.
Study is permanently closed to accrual.

i. Have all subjects completed all research related activities/interventions?

Protocol Title: Conservative versus Suture Repair of Hand and Feet Lacerations in Children

- ii. Will the research only remain active for long-term follow-up of subjects?
- iii. Are remaining research activities limited to data analysis only? (See instructions above).
- iv. For studies that are closed to subject accrual, do any subjects need to be re-consented (to inform them about changes to study procedures, study risks, study personnel, etc.)?

For IRB office use: * may qualify for expedited review

c) The study has expired and needs to be re-initiated.
Explain any research activities occurring during lapse in IRB approval.

2. Date the study was initially approved by the IRB: 06/21/2016

3. Approval date of previous continuing review: 06/05/2018

4. Total number of participants/records/specimens you are approved to enroll: 50

5. Total number of subjects that have given consent (verbal or written) to date: 26

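### Enrolling 50 with 40% attrition leaves 30 evaluable children (15 per group), not the 36 (18 per group) on which the stated 90% power rests

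*Combined protocol and SAP*

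**What the plan says.** The sample-size paragraph in section 3(d) of the protocol makes three linked statements.

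- Requirement: "A sample size of 18 patients per group will be needed to provide a power of 90" per cent, "with 0.05 alpha error to detect a 15mm difference in the VAS".
- Attrition and enrolment: "A patient attrition rate of 40% is expected and with this considered, a total of 50 patients will be enrolled". The sentence goes on to say that this total is what powers the study and that it includes 20 patients from a previous study.
- Analysis: a two-sample t-test, with "A significance level of 0.05 will be used in all analysis". The trial is described as an equivalence trial in which "a non-inferiority average difference of 15mm with the cosmesis VAS scale will be considered clinically equivalent".

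No standard deviation is given, the sidedness of the test is not stated, and the step from 18 per group to 50 is not shown.

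The Continuing Review form carries the same total in item 4: "Total number of participants/records/specimens you are approved to enroll: 50". Items 5 and 7 record 26 consented and accrued. Item 10 reports withdrawals as "N=9; Due to lack of patient returns at 4 months post repair for digital pictures to be obtained".

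**The concern.** An attrition allowance has to be divided out: if a fraction d is lost, the number enrolled is the evaluable number divided by (1 - d). Multiplying by (1 + d) gives too few, and the gap widens as d grows. At 40% it is large, and 50 is close to what the multiplication gives.

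If so, the plan would miss its stated power even with recruitment and follow-up going exactly as assumed. Two features of this trial add weight.

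- The aim is to show no difference in cosmetic outcome, so the power claim bears directly on how a null result is read.
- The same 50 is the approved enrolment total. Section 8(b) of the form says the accrual number should agree with the power analysis in 3(d), and treats going above it as a protocol violation. The error would therefore sit in the enrolment cap as well as in the justification.

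**Working it through.** **Inputs, all from section 3(d) unless noted**

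- Evaluable children needed: 18 per group, 36 in total
- Power 90%, alpha 0.05, difference 15 mm
- Attrition 40%
- Enrolment 50 (also Continuing Review item 4)
- Losses to date: 9 of 26 (Continuing Review items 7 and 10)
- Equal allocation, implied by the equal group sizes

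**Step 1. Reproduce the stated 50**

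- Added on: 36 x (1 + 0.40) = 50.4, which matches 50.
- Divided out: 36 / (1 - 0.40) = 60, which does not.

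**Step 2. What 50 delivers under the plan's own attrition**

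- 50 x (1 - 0.40) = 30 evaluable, or 15 per group.
- Shortfall: 36 - 30 = 6.
- Highest attrition at which 50 still gives 36: 1 - 36/50 = 28%.
- If each child independently has a 40% chance of loss, the probability of 36 or more evaluable out of 50 is 0.054 (exact binomial).

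Steps 1 and 2 need no SD.

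**Step 3. Effect on power**

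The SD has to be inferred from 18 per group, 15 mm and 90% power. For a two-sided t-test at 0.05 the noncentrality is 15 / (SD x sqrt(2/n)), and power is 90% at n = 18 when SD = 13.48 mm. With that SD:

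- n = 18: noncentrality 15 / (13.48 x sqrt(2/18)) = 3.34, power 90%.
- n = 15: noncentrality 15 / (13.48 x sqrt(2/15)) = 3.05, power 83.7%.

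SDs from 13.08 mm (above which 17 per group no longer reaches 90%) to 13.88 mm (the largest that 18 per group supports under the normal approximation) give 85.8% down to 81.5% at 15 per group.

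Because neither the sidedness nor the equivalence procedure is specified, the other readings were checked too, each with the SD that makes 18 per group give exactly 90%:

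| Test assumed | Implied SD (mm) | Power at 15 per group |
|---|---|---|
| Two-sided t, 0.05 | 13.48 | 83.7% |
| Two-sided normal approximation, 0.05 | 13.88 | 84.1% |
| One-sided t, 0.05 | 15.07 | 84.5% |
| One-sided normal approximation, 0.05 | 15.38 | 84.8% |
| Two one-sided t-tests, 0.05 each, true difference 0 | 13.40 | 82.1% |
| Two one-sided t-tests, 0.025 each, true difference 0 | 12.12 | 81.0% |

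No reading restores 90%.

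**Step 4. Attrition reported so far**

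- 9/26 = 34.6%, above the 28% limit.
- Applied to 50: 50 x 17/26 = 32.7, about 33 evaluable. At 16 and 17 per group with SD 13.48 mm, power is about 87%.

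**The case against.** **The 20 carried-over patients.** If most of them had already finished follow-up and the 40% applied only to the 30 new patients, 30 x 0.60 = 18 would remain, and 18 of the 20 earlier patients would bring the total to 36. The Comments section also mentions follow-up data for the first 18 subjects. But section 3(d) describes the 20 only as already enrolled and attaches the 40% to the total of 50. Nothing says that the first 18 subjects came from the earlier study. The reading is possible but unsupported, and if it was intended the sentence still has to say so.

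**The mechanism is inferred.** This stands: no derivation is shown. The shortfall does not depend on how 50 was reached.

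**Missed visits have a fallback.** Section 3(b) provides a phone call, but it collects a 1-to-10 parental satisfaction score. It does not supply the blinded photograph VAS on which the study is powered.

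**Enrolment may be over.** A reply in the Comments section says no more patients will be enrolled, and the Event History shows that approval expired and the third continuing review was withdrawn. With 26 enrolled and 9 lost, about 17 children would be evaluable, and at SD 13.48 mm power would be about 57% (8 and 9 per group). So the corrected figures describe the plan as designed and not what the trial will achieve. That limits the practical reach of the correction but does not make the 90% right. The form itself is unclear on status, since item 1 is marked both open to accrual and on hold.

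**The counts of losses differ.** The form gives 9 of 26, while the Comments section implies 18 + 9 = 27. At 9/27 = 33% the loss still exceeds 28%.

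**The power loss is moderate.** This also stands: about six points, with power still above 80% under every reading.

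**Conclusion.** The concern holds. On the plan's own figures, 50 enrolled yields 30 evaluable children against the 36 required, and 60 would be needed to retain 36. That part is certain and independent of the SD.

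Power as planned is about 84% instead of 90%. This assumes an SD of about 13.5 mm, back-solved from 18 per group with a two-sided t-test. The range is 81% to 86% across the implied SDs and the readings of the test. The type II error rises from 10% to about 16%. The explanation that the allowance was added on is the likely one but is not documented.

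**What to change.** Rewrite the attrition sentence in section 3(d) along these lines:

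> With 50 children enrolled and 40% attrition, 30 (15 per group) are expected to be evaluable. This gives about 84% power for a 15 mm difference, assuming an SD of about 13.5 mm (two-sided t-test, alpha 0.05). Power of 90% would require attrition of no more than 28%, or 60 enrolled.

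The 13.5 mm is a back-calculated placeholder. The investigators should replace it with the SD and sidedness actually used for the 18 per group, and recompute the power if these differ. If the 20 carried-over patients were meant to be exempt from the 40%, say so and give the number with usable photographs. If enrolment has closed, label these figures as the design assumption and report the achieved evaluable number separately.

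The cost is one rewritten sentence and a less favourable power figure. No additional enrolment is needed unless the investigators wish to keep the 90%, which at 40% attrition means seeking approval for 60.

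### Twenty of the planned 50 children come from an earlier, undescribed study (#23300), and the primary t-test has no term for source study

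*Combined protocol and SAP*

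**What the plan says.** Section 3(d) (data analysis and sample size) states, for the contrast between arms on the VAS: "A sample size of 18 patients per group will be needed to provide a power of 90% with 0.05 alpha error to detect a 15mm". It allows for 40% attrition and concludes that "a total of 50 patients will be enrolled in order to power the study", adding that "this will include the 20 patients already enrolled in the previous study (#23300").

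The analysis named for continuous outcomes is: "Differences between groups will be analyzed using the Student's t-test for independent samples". The error rate is given as "A significance level of 0.05 will be used in all analysis", without sidedness. The decision threshold is that "a non-inferiority average difference of 15mm with the cosmesis VAS scale will be considered clinically equivalent".

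No study term, stratification, by-study table or analysis without the 20 appears anywhere. Section 3(b) describes allocation (a computer-generated schedule in sealed packets), photography and rating for the current protocol only. Nothing is said about these matters in #23300.

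On accrual, item 7 of the Continuing Review form reads: "Total number of participants accrued since the beginning of the project: 26". Item 10 reports 9 withdrawals for lack of a 4-month return. In the Comments section, item 5 asks why "follow-up data was able to obtained for the first 18 subjects, but not for the last 9 subjects", and the response to item 3 says that enrolment has ended.

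**The concern.** The primary comparison pools children enrolled under two study numbers. The two groups may differ in calendar period, wound mix, photography or rating conditions, and so in mean VAS. An unadjusted t-test handles such a difference poorly in two ways.

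- The between-study shift is counted as residual variation. This widens the interval that is to be compared with 15 mm.
- If the share of #23300 children differs between the arms, part of the shift appears as a treatment difference.

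There is also a question of what the result would represent. Enrolment has stopped, so the mix of earlier and current children is fixed, and the documents do not let a reader work out what that mix is. It also matters whether the #23300 outcomes had been seen by arm before the margin was chosen, and the documents do not say.

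**Working it through.** **Inputs from the documents.** 20 children from #23300; 50 planned; 18 per arm; 15 mm; alpha 0.05; power 90% (all section 3(d)). 26 accrued and 9 without the 4-month visit (Continuing Review items 7 and 10).

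**Assumptions.** The SD is not stated. The between-study shift is unknown, so 0, 5, 10 and 15 mm are shown. Alpha is taken as two-sided.

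**1. The plan's own figure.** Without an SD, 18 per arm cannot be checked directly. Solving for the SD that gives 90% power by the noncentral t distribution (34 df, two-sided 0.05, 15 mm) gives 13.5 mm. That value is used below. If alpha is one-sided 0.05, the implied SD is about 15.1 mm.

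**2. Loss of precision.** With planned share w = 20/50 = 0.40 and equal allocation in both studies, pooled variance = SD² + w(1 − w) × shift² = 13.5² + 0.24 × shift².

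| Shift (mm) | Pooled SD (mm) | Power, 18 per arm |
|---|---|---|
| 0 | 13.5 | 90% |
| 5 | √(182.25 + 6) = 13.7 | 89% |
| 10 | √(182.25 + 24) = 14.4 | 86% |
| 15 | √(182.25 + 54) = 15.4 | 81% |

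With a study term the residual SD returns to 13.5 mm on 33 df. Power is then 89.9%, the same to one decimal as the t-test with no shift, so the term costs almost nothing if it proves unnecessary.

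**3. Shift carried into the arm difference.** This equals shift × (share of #23300 in one arm − share in the other). Suppose the 20 split 13:7 and the other 30 split 15:15. The arms are then 28 and 22, and a 10 mm shift gives 10 × (13/28 − 7/22) = 10 × (0.464 − 0.318) = 1.46 mm. With a 10:10 split it is zero. Under simple 1:1 randomisation, a 13:7 or more uneven split in either direction has probability 0.263 (binomial, n = 20).

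For scale, the standard error of the arm difference at 28:22 is 13.5 × √(1/28 + 1/22) = 3.8 mm. So 1.46 mm is about 0.4 of a standard error and a tenth of the 15 mm margin.

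**4. Who the completers are.** 26 − 9 = 17 completers. Item 5 of the Comments implies 18 + 9 = 27, which disagrees with 26; 17 is used here.

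- *If the 26 include the 20:* at most 26 − 20 = 6 children are new, so at least 17 − 6 = 11 of 17 (65%) come from #23300. If the 20 were enrolled first and the last 9 were the ones lost, all 17 do.
- *If the 26 exclude the 20:* the earlier children are 20/46 = 43% of those enrolled.

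The Continuing Review form sets 26 against an approved total of 50, and section 3(d) counts the 20 within 50. That makes the first reading plausible, but nothing states it.

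**The case against.** The strongest reply is that if both studies randomised 1:1, the unadjusted t-test is valid. Chance imbalance of the 20 across arms then has expectation zero and is ordinary sampling error, already reflected in the inflated SD. Counting it as a further bias would count it twice. The power loss is also modest, only about one percentage point at 5 mm, and both the SD and the shifts are assumed. The calculation describes the planned 36 evaluable children, not the 17 or so with follow-up. All of this stands, and it limits the point to an inexpensive improvement in precision and transparency.

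The reply depends on #23300 having been validly randomised at the same ratio, and the documents do not say so. A reader might infer that the 20 were separately randomised, so that source study is a formal randomisation stratum. Section 3(d) says only that they were already enrolled. It does not say how they were allocated, or whether one list ran across both study numbers.

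A second objection is that a study term is no help in the extreme case. If every completer comes from #23300 the term cannot be estimated, and with six or fewer new children a by-study comparison says little. This also stands. It is why the description of #23300 and an analysis without the 20 are needed as well as the term.

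**Conclusion.** The point holds as a recommended change to the analysis. Forty per cent of the planned sample comes from a study that the documents do not describe, and the only named primary analysis ignores source study. Given an SD of 13.5 mm and 18 per arm, the cost is about 1, 4 or 9 percentage points of power for shifts of 5, 10 or 15 mm. Confounding of the arm difference is small in the case worked (1.5 mm). It is systematic only if #23300 was not validly randomised at the same ratio.

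Two stronger readings are tempting and are not supported. One is that the trial rests largely on old data. The plan puts the share at 40%; a majority follows only if the 26 accrued include the 20, which is left open. The other is that pooling biases the result. No document shows a between-study shift, unequal allocation or invalid allocation in #23300. What can be said is that the documents do not allow these possibilities to be ruled out.

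**What to change.** - **Primary analysis.** Replace the t-test for cosmesis with a linear model of VAS on arm plus source study (#23300 or current), and base the 15 mm decision on its confidence interval, where both studies contribute completers.
- **Reporting.** Give completers by arm and source study, the arm difference by source study, and a sensitivity analysis without the 20.
- **Description.** State how #23300 allocated patients and at what ratio, its eligibility, photography and rating procedures, and whether its outcomes had been seen by arm before the margin was set. State whether the 26 accrued include the 20, and reconcile 17 with 18 completers.
- **Condition on pooling.** If #23300 was validly randomised at a different ratio, the study term deals with it. If it was not validly randomised, a study term is no cure, and its patients should not be pooled in the primary comparison.

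The cost is one degree of freedom, one small table and a paragraph; no new data are needed. If all completers turn out to come from one study, the term drops out and that fact must be reported.
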